Postoperative pain control is an area of active investigation as inadequate pain management can lead to an increased length of stay, readmission, chronic pain, and opioid dependence.¹⁻³ For laparoscopic hysterectomy, several non-opioid alternatives to pain management have been evaluated in an attempt to reduce patients' pain and minimize opioid consumption. These include local anesthetics, transversus abdominis plane blocks, anticonvulsants, non-steroidal anti-inflammatory medications, and steroids. Non-opioid pain management techniques have demonstrated varying success, with a few methods providing short-term improvements in patients' pain as well as opioid-sparing benefits.⁴ Superior hypogastric plexus block (SHPB) or presacral nerve block is another method that has shown promising results in patients undergoing abdominal hysterectomy; however, has not been evaluated in patients undergoing laparoscopic hysterectomy.

The superior hypogastric plexus lies in the presacral space and supplies autonomic innervation to the pelvis. This plexus has been implicated in chronic pelvic pain with studies demonstrating reduced pain scores and opioid use following image-guided percutaneous blockade or surgical transection of the plexus.⁵⁻⁹ To our knowledge, only one study has investigated the efficacy of a SHPB at the time of hysterectomy.¹⁰ This study was a double-blind randomized controlled trial of 68 women undergoing an abdominal hysterectomy, randomized to a presacral injection of 20 mL of ropivacaine versus saline. Sixty-three percent of women in the ropivacaine group had a VAS pain score less than 4 at two hours postoperatively, compared to 25% in the placebo group ($p=0.015$). Median opioid consumption was also less at 55.8 mg for the treatment group versus 72.4 mg for the placebo group ($p=0.032$). There were no side effects or adverse events reported in this study. We hypothesize that a SHPB will provide similar benefits in patients undergoing a laparoscopic hysterectomy.

VII. Objectives:

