and the incisional block will contain 50 mg of bupivacaine (20 mL of 0.25% bupivacaine, 2.5 mg/mL) for a total dose of 75 mg. The maximum safe dose of bupivacaine is 2 mg/kg therefore all patients with a weight over 37.5 kg (82.5 lbs) will be safe to receive this dose. This weight threshold encompasses nearly all women over age 18. In the very unlikely event that a patient weighs less than this, the incisional block will be reduced accordingly. No additional bupivacaine will be used during the procedure. Patients with an allergy to bupivacaine will be excluded from the study.

Patients will be charged for the bupivacaine anesthetic as it is a standard component of a laparoscopic hysterectomy and is routinely injected in the incisions for local anesthesia. All patients will be receiving the anesthetic in the incisions regardless of the treatment arm. Only patients in the SHPB arm will also receive the anesthetic in the presacral space. This is not anticipated to add cost to the procedure as all patient in the study will receive this medication.

XII. Outcomes:

The primary outcome will be immediate postoperative patient pain scores (within 4 hours) using the Visual Analog Scale (VAS) in the recovery unit. The secondary outcomes will be intraoperative and postoperative opioid consumption as well as VAS pain scores from the Brief Pain Inventory (BPI) as recorded in a patient diary for one week following surgery. Subgroup analyses will be performed on patients undergoing a hysterectomy for pelvic pain and patients who undergo a laparoscopic hysterectomy without concomitant procedures.

XIII. Participant timeline:

Participation starts with enrollment and an eligibility screen. Eligible patients who agree to participate will be consented on the day of surgery. Patients will undergo surgery and be followed up to eight weeks postoperatively.

XIV. Sample size:

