A sample size was determined using prior data on the increased percentage of patients with low VAS scores following SHPB and abdominal hysterectomy.¹⁰ Sixty-three percent of women in the ropivacaine group had a VAS pain score less than 4 at two hours postoperatively, compared to 25% in the placebo group ($p=0.015$). A two-sample comparison of proportions with a beta error of 0.2, alpha error of 0.05, and 10% loss to follow-up, therefore requires a sample size of 58 patients. Accounting for heterogeneity in the patient population we aim to recruit 100 patients, with 50 in each treatment arm. Patients will be enrolled at BWH, FH, UNC and GWU, with approximately 50 patients coming from BWH/FH, 30 patients from UNC and 20 patients from GWU. We expect to enroll approximately 20 patients per month between the three sites. Data collection is anticipated to take approximately seven months, accounting for postoperative evaluation up to eight weeks after surgery.

XV. Recruitment:

Recruitment begins at the initial consult visit. The surgeon will explain the study, and then ask the patient if they would like to hear more about it. Only patients that affirm that they are

interested will then be given a description of the study protocol and a copy of the consent form to take home with them (Appendix “SHPB Consent Form”). If a subject decides they do not want to participate, a decline card will be included in the materials. A research assistant will also contact subjects by phone to answer any questions regarding the study. Patients who remain interested in participating will be formally consented on the day of surgery by one of the participating surgeons.

XVI. Assignment of interventions, allocation concealment, and implementation:

Patients will be randomized on the day of surgery after informed consent has been obtained. Subjects will be randomized using urn randomization with a 1:1 allocation of treatment and placebo, stratified by the three sites (BWH/FH, UNC and GWU). Randomized allocation of the treatment arms will be concealed in sequentially-numbered, opaque, sealed envelopes. The randomization sequence and concealed allocation envelopes will be prepared by a research assistant and unknown to the remainder of the study staff.

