Patients will be randomized to two treatment groups: one group will receive the SHPB, and the other will receive no block. Patients will be randomized after informed consent is confirmed on the day of surgery. Subjects will be randomized using urn randomization with a 1:1 allocation of treatment and placebo, stratified by the three sites (BWH/FH, UNC and GWU). Randomized allocation of the treatment arms will be concealed in sequentially-numbered, opaque, sealed envelopes. The randomization sequence and concealed allocation envelopes will be prepared by a research assistant and unknown to the remainder of the study staff. A placebo arm (e.g. presacral injection of saline) was not designated given little to no anticipated benefit of a sham block. For the treatment arm, the risks of presacral injection are anticipated to be very rare and superseded by the potential benefit of reduced postoperative pain as demonstrated in patients undergoing abdominal hysterectomy.¹⁰

XVII. Blinding:

Patients will be blinded to the treatment arm; however, the surgeon and operating room staff will know if a patient has been randomized to receive the block during the hysterectomy. Nurses in the recovery unit and on the inpatient floors will also be blinded to the treatment arm. The Medication Administration Record will document a blinded medication for patients in the trial to reduce the risk that staff caring for patients outside the operating room become aware of the treatment arms.

XVIII. Data collection methods:

Postoperative pain scores will be collected by a registered nurse upon admission to the recovery unit, and at every hour for four hours or until the patient is discharged. Most patients are discharged home on the same day as surgery with a recovery unit stay between two to six hours depending on the patient. If a patient is admitted to the hospital, the worksheet will be completed by the recovery unit nurse for as long as the patient is in the recovery unit and completed by the floor nurse for a total of four hours postoperatively. Pain scores will be

collected using the Visual Analog Scale to ask patients their pain level on a scale of 0 to 10, where 0 indicates no pain and 10 indicates the worst pain imaginable.

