Intraoperative and immediate postoperative opioid consumption will be collected from the Medication Administration Record. The nursing staff will also be asked to complete a recovery worksheet that details the VAS pain score and opioid administration on admission to the recovery unit and every postoperative hour until four hours or the patient is discharged (Appendix “SHPB RN Worksheet”). The nursing staff will also be asked to note the total time the patient was in the recovery unit. Patients will also be asked to complete a daily diary for one week following the procedure, which details their pain level and daily opioid consumption (Appendix “SHPB Patient Diary”).

Patients will be followed for eight weeks after surgery to assess for the occurrence of any postoperative complications. Detailed patient and procedure characteristics including age, race, body mass index, parity, surgical history, surgery indication, procedure type, and surgical approach will also be collected.

No additional follow-up visits will be required; however, the patient will be asked to return their postoperative diary at their routine postoperative visit (approximately four weeks after surgery). To avoid loss to follow-up, patients will be contacted one to three days after surgery or discharge to remind them to complete the daily diary for one week postoperatively. Patients who have a prolonged hospital stay or who are readmitted to the hospital during the first postoperative week will be reminded to complete the diary as an inpatient, and their narcotic consumption obtained from the medical record. Patients who do not schedule a routine postoperative visit or who forget to bring the diary to their postoperative visit will be contacted by phone or mail and a stamped and addressed envelope sent to their home address for them to return the diary.

XIX. Data management:

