All healthcare personnel involved in this study will be responsible for completing correct operative and postoperative data. Patients will be asked to complete a daily postoperative diary which they will return at their postoperative visit. All other data points will be abstracted from patient medical records by research assistants. A minimum number of persons will be involved with the data abstraction in an attempt to decrease introduction of bias. The research assistants will also keep a copy of all source documents such as informed consent on file. All data will be kept in password-protected computer systems, locked file cabinets, and offices accessible only to study staff.

XX. Statistical methods:

Statistical analysis will be performed to test the null hypothesis that there is no difference in VAS pain scores or opioid consumption following laparoscopic hysterectomy with and without a SHPB. The primary analysis will be intention to treat, i.e. those patients randomized to the two treatment arms regardless of the intervention or outcome assessment. The primary outcome (immediate postoperative VAS pain scores in the recovery unit for four hours) will

be treated as continuous as well as dichotomized variables and compared using Student's t-tests if continuous and normally distributed, Wilcoxon tests if continuous and non-normally distributed, and Chi-square tests if dichotomized. A linear regression will be performed to adjust for the two participating sites. As patients are randomized to the two treatment groups, no additional adjustment for potential confounding variables is anticipated to be necessary. Subgroup analyses will be performed on patients undergoing a hysterectomy for pelvic pain and patients who undergo a laparoscopic hysterectomy without concomitant procedures. The final analysis will be conducted at the 0.05 level of significance and the interim analysis will be conducted at the 0.002 level of significance (to minimize type I error). Statistical analysis will be performed using appropriate statistical software and with the assistance of a biostatistician.

XXI. Data monitoring:

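### Section XX names no single primary analysis: the VAS outcome is tested as continuous and as dichotomized at one unsplit 0.05, with lead coding, time point or summary, and cut-off all left open

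*Combined protocol and SAP*

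**What the plan says.** - **Outcome (XII. Outcomes).** "The primary outcome will be immediate postoperative patient pain scores (within 4 hours) using the Visual Analog Scale (VAS) in the recovery unit". This gives a window, not a time point or a per-patient summary.
- **Measurement (XVIII. Data collection methods).** Nurses record a score on arrival in recovery and then "at every hour for four hours or until the patient is discharged"; the nurse worksheet is described as covering "every postoperative hour until four hours or the patient is discharged". That is up to five scores per patient, and fewer for a patient who leaves early. The same section puts typical recovery stays at two to six hours.
- **Analysis (XX. Statistical methods).** The scores will "be treated as continuous as well as dichotomized variables and compared using" a t-test or Wilcoxon test when continuous and a chi-square test when dichotomized. Then: "A linear regression will be performed to adjust for the two participating sites". For alpha: "The final analysis will be conducted at the 0.05 level of significance", with 0.002 for the interim. Section XX uses the term primary analysis only to fix the intention-to-treat population.
- **Sizing (XIV. Sample size).** The basis is the prior abdominal-hysterectomy trial: "Sixty-three percent of women in the ropivacaine group had a VAS pain score less than 4 at two hours postoperatively", against 25% on placebo. The method is given as: "A two-sample comparison of proportions with a beta error of 0.2, alpha error of 0.05, and 10% loss to follow-up". The result is 58, raised to 100.

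**The concern.** Section XX commits to both codings, since it joins them with words that mean in addition. It gives neither a ranking nor a decision rule. Its conditional wording settles only t-test against Wilcoxon, by normality. Three other choices are also open: which of up to five scores (or which summary of them) is tested, where the cut lies, and whether the unadjusted test or the site-adjusted regression carries the conclusion.

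Two things are at stake. First, the error rate attached to the trial's one confirmatory claim depends on a rule that is not written down. Second, someone who has seen the results could present whichever coding, hour or cut-off is more favourable as the primary result, and the protocol would not contradict them. The same gap affects the mid-point analysis, because the 0.002 threshold is not tied to a named test either.

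**Working it through.** **1. The plan's own figure.** Inputs from XIV: 0.63 and 0.25, power 0.80, alpha 0.05 (sidedness not stated; two-sided reproduces the result), 10% loss. With pooled variance and mean rate 0.44:

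n per arm = [1.96·√(2·0.44·0.56) + 0.842·√(0.63·0.37 + 0.25·0.75)]² / 0.38² = 25.6, so 26 per arm and 52 in total. 52/0.9 = 57.8, so 58. The figure reproduces. The formula uses two rates only; the cut-off and the hour enter through the source of those rates.

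**2. Power at the planned size.** 50 per arm, or 50 × 0.9 = 45 after loss. Exact power of the uncorrected chi-square for 63% vs 25% is 80.3% at 26, 96.0% at 45 and 97.9% at 50 per arm. If scores are normal, the same rates imply a shift of 1.006 SD, and a t-test has 99.7% power at 45 and 99.9% at 50. Either coding is adequately powered at the assumed effect.

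**3. Type I error, large-sample calculation.** For normal scores with a share p below cut-off c (in SD units), the two test statistics have correlation φ(c)/√(p(1−p)). At p = 0.44 this is 0.394/0.496 = 0.795. The bivariate normal then gives P(both significant) = 2.16%, so P(either) = 5 + 5 − 2.16 = 7.84%. For p from 0.25 to 0.75 the correlation is 0.73-0.80, either is 7.8-8.2% and both is 1.8-2.2%. If the tests were independent, either would be 1 − 0.95² = 9.75%.

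**4. Simulation.** The documents give no VAS SD or mean, so these inputs are assumptions: integer 0-10 scores, SD 2.5, control mean 4, 4.5 or 5, cut-off below 4, one score per patient, 50 per arm, t-test against chi-square, 40,000 replicates per setting. Shifts are applied before rounding to the 0-10 scale.

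| | Uncorrected chi-square | Continuity-corrected |
|---|---|---|
| No effect: either coding significant | 8.0-8.1% | 6.6-6.7% |
| No effect: both significant | 2.0-2.5% | 1.5-1.9% |
| Shift 1.0-1.5 points: exactly one significant | 19-24% | 24-28% |
| Shift 2.0 points: exactly one significant | 8-10% | 12-14% |

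At the sizing effect (about 1.0 SD, or 2.5 points here) exactly one coding is significant in about 2-7% of trials, over a wider set of settings that also includes 45 per arm and the Wilcoxon test.

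**5. Sensitivity to the cut-off.** With about 8% or 84% of scores below the cut, either stays at 6.0-8.8%, but both falls to about 0.3-1.6%. The figure for both is therefore specific to a mid-range cut-off.

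**The case against.** The strongest reply is that XIV already points to the endpoint: the trial was sized on VAS below 4 at two hours, so that should be read as primary. It is a natural candidate, but XIV reports it as the prior trial's result and borrows its rates. XII describes a four-hour window, and XX lists the continuous coding first and gives no cut-off. Either coding could be defended as primary.

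A second reply is that both codings would be run and reported, so nothing is hidden. That is fair. The gap is in which result leads, and in the hour, summary and cut-off behind it.

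A third is that the codings seldom disagree at the sizing effect. This also stands. The disagreement figures of 19-28% need a true shift of 1.0-1.5 points (0.4-0.6 SD at the assumed SD), which the documents do not posit. It does not settle the type I question.

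Some stronger readings are not supported:

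- A reader might infer that the plan lets either coding win and so inflates the error rate. No such rule is stated, and no both-must rule either.
- A reader might infer a larger inflation from testing every hour in both codings. The text does not propose that. Any calculation on five complete scores would also ignore that scoring stops at discharge.
- A reader might infer that the trial is underpowered. Step 2 shows otherwise.

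**Conclusion.** The point holds. Followed as written, Section XX produces several tests of the primary outcome under one unsplit 0.05 with none designated to carry the conclusion, so the primary type I error is not fixed at 5% and the lead result is open to choice after the data are seen. That conclusion rests on the text alone.

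The percentages only illustrate it. A false-positive rate of about 6.5-8% (either coding) or 1.5-2.5% (both) depends on the assumed integer scale, SD 2.5, one fixed score and a cut-off below 4. Those rates cover the choice of coding only; they do not count the open hour or summary, the site-adjusted regression or the interim look. They should not be quoted as the trial's actual error rate.

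**What to change.** In XII and XX, pre-specify one primary analysis at the final alpha, before the mid-point analysis. Either choice is sound if made in advance:

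- **Binary:** the proportion with VAS below 4 at the two-hour score. This matches the sizing and keeps 96.0% power at 45 per arm and 97.9% at 50 for 63% vs 25%.
- **Continuous:** the two-hour score, or one defined four-hour summary (closer to XII), in a linear model with treatment and site. Site needs three levels, because XVI stratifies by three sites while XX refers to two.

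Label the other coding supportive and the other hours secondary. State how a patient discharged before the primary score, or before the summary is complete, is handled. If the nurse worksheet does not already fix it, state whether hours count from the end of surgery or from arrival in recovery.

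The cost is wording only, with N unchanged. The sponsor gives up several chances at significance for one declared test. The binary option is also less sensitive to effects smaller than assumed: at a 0.5 SD shift and 50 per arm, with normal scores and 25% of controls below 4, chi-square power is 48.0% against 69.7% for the t-test.

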The objective of this study is to assess the efficacy of a SHPB for pain relief following laparoscopic hysterectomy. The superior hypogastric plexus lies in the presacral space and supplies autonomic innervation to the central pelvis. This plexus is suspected to play a role in postoperative pain following a hysterectomy. We hypothesize that a SHPB using the anesthetic bupivacaine will reduce patients' pain scores and opioid consumption following a laparoscopic hysterectomy.

VIII. Trial design:

This study is designed as a multi-center, randomized, single-blind, controlled trial of patients scheduled for a laparoscopic hysterectomy. Patients will be randomized to two groups: one group will receive a SHPB and laparoscopic hysterectomy, and the other will receive no block and laparoscopic hysterectomy.

METHODS

IX. Study setting:

The study will be conducted at three sites: Brigham and Women's Hospital (BWH)/Brigham and Women's Faulkner Hospital(FH), University of North Carolina Medical Center (UNC) and George Washington University (GWU).

X. Eligibility criteria:

Patients over 18 years of age who are scheduled for a laparoscopic hysterectomy at participating sites will be recruited to participate. Patients of all comorbidities will be eligible for inclusion; specifically, patients with chronic pain syndromes will not be excluded so as to evaluate the efficacy of SHPB in this population. The exclusion criteria include patients who are unwilling to consent, who have an allergy to block medications used in the trial, are undergoing a sacrocervicopexy or a sacrocolpopexy, are undergoing a laparotomy, or those with anatomy that limits the safe application of a presacral injection (per the surgeon's discretion at the time of the procedure). Patients will not be excluded if they undergo other concomitant procedures during laparoscopic hysterectomy. While concomitant procedures may contribute to patients' pain following laparoscopic hysterectomy, this will improve the external validity of the trial. Moreover, randomization should balance differences in patients and procedures between the two treatment arms.

XI. Interventions:

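### The site adjustment names two sites although three enroll and define the randomization strata, and the plan does not say whether the adjusted or the unstratified analysis decides the primary outcome

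*Combined protocol and SAP*

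**What the plan says.** All references are to the combined protocol and SAP.

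- **Number of sites.** Section IX: "The study will be conducted at three sites". Section XIV plans "approximately 50 patients coming from BWH/FH, 30 patients from UNC and 20 patients from GWU" and adds "We expect to enroll approximately 20 patients per month between the three sites".
- **Randomization.** Section XVI describes urn randomization, 1:1, "stratified by the three sites (BWH/FH, UNC and GWU").
- **Adjusted analysis.** Section XX: "A linear regression will be performed to adjust for the two participating sites". It names no sites, and no section defines a two-site grouping.
- **Unadjusted analyses.** Section XX says the primary outcome will "be treated as continuous as well as dichotomized variables and compared using" Student's t-tests if normally distributed, "Wilcoxon tests if continuous and non-normally distributed, and Chi-square tests if dichotomized". None of these is stratified by site.
- **Error level.** Section XX: "The final analysis will be conducted at the 0.05 level of significance". The level is not attached to a particular test or model. Section XX calls the primary analysis intention to treat, which fixes the population and not the test.

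**The concern.** There are two linked gaps.

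First, the only adjusted model in the plan does not match the design. A two-category site term forces two of the three strata together, and the plan gives no basis for choosing which two.

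Second, the plan contains unstratified tests and a site-adjusted regression but one significance level, and does not say which analysis is held to it. The two can fall on opposite sides of 0.05. If the choice is made after the data are seen, the false-positive rate rises above that of either analysis alone.

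**Working it through.** **1. Site count.** Section IX: three. Section XIV: 50 + 30 + 20 = 100 patients at three sites. Section XVI: three strata. Section XX: two. Counting BWH and FH separately gives four hospitals, so that does not explain the figure.

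**2. The plan's sample size.** Inputs from section XIV: 63% vs 25%, alpha 0.05, power 0.80, 10% loss. With a two-sided test, pooled variance and no continuity correction, the mean proportion is 0.44 and

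n per arm = [1.960 × √(2 × 0.44 × 0.56) + 0.842 × √(0.63 × 0.37 + 0.25 × 0.75)]² / 0.38² = (1.376 + 0.546)² / 0.1444 ≈ 25.6, so 26.

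Total 52; 52 / 0.9 = 57.8, so 58. The stated figure reproduces. It does not depend on how site is handled.

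**3. Assumptions for the comparison.** The documents give no site means or VAS SD, so the share of VAS variance due to site is assumed to be 0%, 5% or 10%. Site means are 0, s and 2s with weights 0.5, 0.3 and 0.2. The between-site variance is (0.3 + 0.8)s² − (0.7s)² = 0.61s². At a 10% share s = √(0.10 / 0.61) = 0.405, so the extreme sites differ by 0.81 SD. VAS is taken as normal with total within-arm variance 1, and tests as two-sided (section XX does not state sidedness).

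Effects considered:
- none;
- 0.566 SD, which gives the t-test 80% power at 50 per arm (illustrative, not from the documents);
- the planning effect on a normal scale, z(0.63) − z(0.25) = 0.332 + 0.674 = 1.006 SD.

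**4. Simulation.** 400,000 trials per scenario, N = 100, sites 50/30/20, urn randomization within site. The t-test (98 df) is compared with a linear model with treatment and three-level site (96 df). Monte Carlo SE is at most 0.07 points.

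| Effect | Site share | t-test rejects | Three-site model rejects | Either rejects | Opposite conclusions |
|---|---|---|---|---|---|
| None | 0% | 4.99% | 4.97% | 5.34% | 0.72% |
| None | 5% | 4.70% | 5.09% | 5.59% | 1.39% |
| None | 10% | 4.25% | 5.03% | 5.58% | 1.89% |
| 0.566 SD | 0% | 79.87% | 79.58% | 80.59% | 1.73% |
| 0.566 SD | 5% | 80.26% | 81.59% | 82.63% | 3.40% |
| 0.566 SD | 10% | 80.64% | 83.62% | 84.58% | 4.90% |
| 1.006 SD | 0% | 99.87% | 99.87% | 99.88% | 0.02% |
| 1.006 SD | 5% | 99.89% | 99.91% | 99.93% | 0.04% |
| 1.006 SD | 10% | 99.90% | 99.94% | 99.95% | 0.05% |

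At 0.566 SD, adjustment changes power by 79.58 − 79.87 = −0.3, 81.59 − 80.26 = +1.3 and 83.62 − 80.64 = +3.0 points.

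**5. Two-category coding.** Under the same site means, the between-site variance captured depends on the merge:
- UNC with GWU: 0.5 × 0.5 × (1.4s)² = 0.49s², or 80% of 0.61s².
- BWH/FH with UNC: 0.8 × 0.2 × (1.625s)² = 0.42s², or 69%.
- BWH/FH with GWU: 0.7 × 0.3 × (0.429s)² = 0.039s², or 6%.

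In a separate run of 100,000 trials (10% share, 0.566 SD), power was 80.7% to 83.2% across the merges, against 83.7% with three levels: a loss of 0.5 to 3.0 points. At a 5% share, a run of 40,000 trials gave a loss of 0 to 1.5 points. The type I error of the two-category models was 4.4 to 5.1%.

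**6. Skewed scores.** With assumed skewed integer scores from 0 to 10 (skewness 1.1 to 1.6, 8 to 22% zeros; 200,000 trials each), the three-site linear model rejects in 4.9 to 5.1% of trials under no effect.

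**The case against.** The strongest reply is that this is one stale word. Section XVI names the three strata, no two-site grouping appears anywhere, and section XX provides for a biostatistician, so three levels is the obvious intention. That stands. A reader might infer that an analyst could not work out how to code site, and the documents do not support so strong a claim. The phrase still sits in the only sentence that specifies the adjusted model.

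The second reply is that section XX applies the t, Wilcoxon and chi-square tests to the primary outcome and puts the regression in a later sentence, so the natural reading makes the regression supportive. That reading is reasonable, but the text does not state it. Declaring the unstratified tests primary would also close this gap. The reason to prefer the site-adjusted analysis is that it matches the strata already used.

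Two further inferences should be resisted. One is that ignoring the strata makes the t-test invalid. It is slightly conservative when sites differ. The other is that the 5.3 to 5.6% covers every test in section XX. It covers the t-test and three-site model only. If any of the four analyses may count, the rate is about 9%, with an assumed chi-square cut-point at 25% of the control arm. Most of that excess comes from the open choice between continuous and dichotomized forms, which is a separate issue.

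**Conclusion.** The point holds and is minor. The mismatch between two and three sites follows from the text alone. So does the absence of a statement on which analysis is tested at 0.05.

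The size rests on assumed site shares of variance, normal scores and the planned 50/30/20 split. Within those assumptions, the t-test's error rate falls from about 5.0% to 4.3% as site differences grow, and leaving the choice of this pair open adds 0.3 to 0.6 points to the nominal 5%. At the planning effect the two analyses disagree in at most 0.05% of trials. Power matters only at smaller effects, and there by about 3 points at most. A Cochran-Mantel-Haenszel analysis of the dichotomized form was not simulated. The figures of 58 and 100 patients stand.

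**What to change.** In section XX:

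1. Replace the reference to two sites with *the three participating sites (BWH/FH, UNC and GWU)*.
2. Add: *For the designated form of the primary outcome, the deciding comparison at the 0.05 level takes account of these three sites: a linear model with treatment and three-level site if the form is continuous, or a Cochran-Mantel-Haenszel test stratified by site if it is dichotomized. The unstratified t, Wilcoxon and chi-square tests are supportive.*

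This does not choose the VAS time point, nor between the continuous and dichotomized forms. That needs its own decision, and section XIV sizes the trial on the dichotomized form (VAS below 4).

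The cost is one phrase and two sentences, made before outcome data are analysed. Site is known for every patient, so no data, visits or patients are added. The statistical downside for the linear model is two degrees of freedom (98 to 96), about 0.3 points of power if sites do not differ.

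### Section XX plans no adjustment beyond site because patients are randomized; the comparison stays valid, but a pre-specified baseline covariate model would recover precision at almost no cost

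*Combined protocol and SAP*

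**What the plan says.** Section X does not exclude concomitant surgery: "Patients will not be excluded if they undergo other concomitant procedures during laparoscopic hysterectomy". It accepts that this may matter for the outcome ("While concomitant procedures may contribute to patients' pain following laparoscopic hysterectomy") and relies on allocation to deal with it: "Moreover, randomization should balance differences in patients and procedures between the two treatment arms".

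Section XVI stratifies by site and nothing else: "Subjects will be randomized using urn randomization with a 1:1 allocation of treatment and placebo, stratified by the three sites". Section XVIII lists the data to be collected: "Detailed patient and procedure characteristics including age, race, body mass index, parity, surgical history, surgery indication, procedure type, and surgical approach".

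Section XX compares VAS by t-test, Wilcoxon test or chi-square test, depending on its form and distribution. It adds one regression: "A linear regression will be performed to adjust for the two participating sites". It then closes the matter of covariates: "As patients are randomized to the two treatment groups, no additional adjustment for potential confounding variables is anticipated to be necessary".

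Two further provisions bear on the point. Section XIV raises the total from 58 to 100 to allow for a heterogeneous population. Sections XII and XX plan a subgroup analysis of patients who have no concomitant procedure.

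**The concern.** The plan names a possible influence on pain, collects procedure type and indication, and leaves both out of the treatment comparison. Its reason is that patients are randomized. That answers systematic confounding, but there are two other reasons to adjust.

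The first is precision. If procedure mix affects VAS, it adds to the residual variance however well the arms are balanced.

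The second is chance imbalance. Stratifying by site does nothing to equalize procedure mix, and in a trial of 100 the arms can differ noticeably. The unadjusted estimate then moves with the imbalance.

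At stake are some power and some protection against an unlucky allocation. The validity of the test is not at stake.

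**Working it through.** **The plan's own figure.** Inputs from section XIV: 63% against 25%, alpha 0.05, power 0.80, 10% loss. The section does not say whether the test is one- or two-sided; two-sided is taken here. With the pooled-variance formula and no continuity correction,

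n per arm = [1.96·√(2·0.44·0.56) + 0.842·√(0.63·0.37 + 0.25·0.75)]² / 0.38² = 25.6, so 26.

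The total is 52, and 52/0.9 = 57.8, so 58, as stated. On the same rates, power is 97.8% at 50 per arm and 96.5% at 45 per arm. This concerns VAS dichotomized at 4; the documents give no power for continuous VAS.

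**Assumptions.** The documents supply none of the following:
- 30% to 50% of patients have a concomitant procedure.
- It shifts VAS by 1 to 2 points.
- The SD of VAS is 2.5, with one VAS value per patient.
- The true treatment difference is 1.5 points.
- 45 patients per arm are evaluable (50 less 10%).

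**Variance explained.** R² = p(1−p)·shift²/SD².
- Low end: 0.3·0.7·1²/6.25 = 0.034.
- High end: 0.5·0.5·2²/6.25 = 0.16.

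**Equivalent sample size.** 100/(1−R²) = 103.5 at the low end and 119 at the high end, so adjustment is worth about 4 to 19 patients.

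**Power.** Two-sample t, 45 per arm, difference 1.5, residual SD 2.5·√(1−R²):

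| R² | Power |
|---|---|
| 0 (unadjusted) | 80.4% |
| 0.034 | 81.7% |
| 0.10 | 84.3% |
| 0.16 | 86.7% |

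A simulation at 50 per arm (10,000 runs, frequency 50%, SD 2.5, difference 1.4) agrees. Power goes from 80% to 81% for a 1-point shift and from 80% to 85% for a 2-point shift.

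**Chance imbalance.** Exact binomial, two arms of 45, frequency 30% to 50%. The arms differ by at least 10 percentage points in 30% to 34% of trials and by at least 15 points in 13% to 17%. The effect on the estimate is gap × shift:
- 10-point gap: 0.1 to 0.2 VAS points.
- 15-point gap: 0.15 to 0.3 VAS points.

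The standard error of the difference is 2.5·√(2/45) = 0.53, so these movements are modest.

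**Validity.** In the same simulation, the type I error of the unadjusted test was 4.9% (1-point shift) and 5.3% (2-point shift). Among trials with a gap of at least 20 points it was about 6% and 12%. At 50 per arm, such gaps occur in about 4% to 6% of trials.

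**Sensitivity.** Widening the assumptions to a shift of 0.5 to 2 points and SD 2 to 3 gives R² of about 0.01 to 0.25. Where the unadjusted test has 80% power at 50 per arm, adjustment then gives about 80% to 90%.

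**The case against.** The strongest reply is that nothing here is wrong. An unadjusted randomized comparison already carries chance imbalance in its standard error, its type I error is nominal, and the plan states its choice in advance. That stands. A reader might infer from the lack of adjustment that the primary comparison is biased or invalid; the simulation does not support this.

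Nor do the documents make concomitant procedures a known source of VAS variation. Section X says only that they may contribute and gives no effect size. Every figure for the gain is therefore conditional, and at the low end the gain is about one point of power.

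The increase from 58 to 100 also counts for the plan. It is larger than the 4 to 19 patients at issue, and on the section XIV rates the dichotomized comparison is well powered. It does not remove imbalance, however, and it leaves the power for continuous VAS unstated.

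The subgroup analysis shows that procedure mix was not ignored. It does not repair the primary comparison, because it uses only some of the patients. As worded, it also depends on the surgery performed.

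Two other inferences go too far. The word *anticipated* might be read as leaving room to pick covariates once an imbalance is seen, but its ordinary sense is that none are planned. Nor do the documents say that concomitant procedures are chosen after allocation. They say only that patients are randomized on the day of surgery and that the surgeon knows the arm. That is enough to prefer a covariate fixed before allocation, but it is no evidence that surgeons would act on the knowledge.

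**Conclusion.** The point holds as one of efficiency and pre-specification. The reason given in section XX does not bear on precision or chance imbalance, and a better analysis is available at little cost.

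Under the main assumptions, the gain is about 1 to 6 points of power from a base of 80%. The imbalances considered would move the estimate by 0.1 to 0.3 VAS points against a standard error of 0.53. If the covariates prove weakly prognostic, the gain is negligible. The change is worth making before the data are seen, but the trial's conclusions would not be unsound without it.

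**What to change.** In section XX:

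1. Name a linear model as the primary analysis of continuous VAS. It should contain treatment, the three randomization sites, booked concomitant procedure (yes/no) and a small fixed set of baseline covariates already collected, for example age or pelvic pain indication. Adding covariates to a regression that merely sits beside the t, Wilcoxon and chi-square tests would leave the primary comparison unchanged.
2. Keep the unadjusted test as a sensitivity analysis.
3. Replace the sentence that declines further adjustment with the covariate list and a statement that none will be added after the data are seen.
4. Reconcile the regression's two sites with the three used to stratify randomization.

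Record the booked concomitant procedure before the envelope is opened, and use it in place of the procedure performed. The operating surgeon knows the arm, so a variable settled during surgery is not protected by randomization.

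The cost is wording in section XX, one tick-box before allocation and a few degrees of freedom out of about 90 patients.
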